9.2.1 Other Informed Consent Procedures

Illiterate Subjects

If illiterate, subjects will be consented according to the procedures approved by the reviewing IRB.

9.3 Consent for Secondary Use of Stored Specimens and Data

Residual samples/specimens are those that are left over after protocol-specified testing and this study has been completed. As part of the main consent form, subjects enrolled in this study will consent to remaining (residual) blood and sputum specimens being kept for possible use in secondary research studies. Residual specimens will be stored coded in the ARLG Biorepository, until released for secondary research. The researchers using the samples/specimens will not be able to link the samples back to subjects or directly identify subjects. No human genetic testing will be performed on these residual samples/specimens. The recipients of specimens will be informed that these specimens have an NIH certificate of confidentiality. Use of the specimens for secondary research unrelated to this study will require review by an IRB.

9.4 Exclusion of Women, Minorities, and Children (Special Populations)

Children will be excluded from this trial as the study entry criteria only allows enrollment of adults. Non-English speakers, illiterate individuals, and non-writing individuals will be allowed to participate in the study, provided the reviewing IRB approves methods and materials given to subjects, to include but not limited to the written informed consent written in the language understandable to the subject. Women and minorities will not be excluded from participation provided all study entry criteria are met. Investigational sites should follow the direction of the reviewing IRB prior to enrollment of subjects considered to be “vulnerable”.

9.5 Subject Confidentiality

Subject confidentiality is strictly held in trust by the participating investigators, their staff, and the sponsor(s) and their agents. This confidentiality includes documentation, investigation data, subject's clinical information, and all other information generated during participation in the study. No information concerning the study or the data generated from the study will be released to any unauthorized third party without prior written approval of the sponsor. Subject confidentiality will be maintained when study results are published or discussed in conferences.

All information provided by the sponsor and all data and information generated by the participating sites as part of this trial (other than a subject's medical records) will be kept confidential by the site PI and other study personnel to the extent permitted by law. This information and data will not be used by the site PI or other study personnel for any purpose other than conducting this trial. These restrictions do not apply to: (1) information which becomes publicly available through no fault of the site PI or other study personnel, (2) information which is necessary to disclose in confidence to an IRB solely for the evaluation of this trial, (3) information which is necessary to disclose in order to provide appropriate medical care to a study subject, or (4) study results which may be published as described in Section 15 Publication Policy.

The study monitor or other authorized representatives of the sponsor or governmental regulatory agencies may inspect all documents and records required to be maintained by the investigator, including but not limited to, medical records (office, clinic, or hospital) and pharmacy records for the subjects in this study. The clinical study sites will permit access to such records.

All records will be kept locked and all computer entry and networking programs will be carried out with coded numbers only and with password protected systems. All non-clinical specimens, evaluation forms, reports, and other records that leave the site will be identified only by a coded number.

9.6 Certificate of Confidentiality

To protect privacy, the NIH provides a Certificate of Confidentiality. With this Certificate, the researchers cannot be forced to release information that may identify the research subject, even by a court subpoena, in any federal, state, or local civil, criminal, administrative, legislative, or other proceedings. The researchers will use the Certificate to resist any demands for information

that would identify the subject, except as explained below.

The Certificate cannot be used to resist a demand for information from personnel of the US Government that is used for auditing or evaluation of federally funded projects, like this study, or for information that must be released in order to meet the requirements of the FDA.

A Certificate of Confidentiality does not prevent the subject from voluntarily releasing information about themselves or their involvement in this research. If any person or agency obtains a written consent to receive research information, then the researchers may not use the Certificate to withhold that information.

The Certificate of Confidentiality does not prevent the researchers from reporting without the participant's consent, information that would identify the participant as a participant in the research project regarding matters that must be legally reported including: child and elder abuse, sexual abuse, or wanting to harm themselves or others.

The release of individual private information or specimens for other research will only occur if consent was obtained from the individual to whom the information, document, or biospecimen pertains, for the purposes of other research that is compliant with applicable Federal regulations governing the protection of human subjects in research.

9.7 Costs, Subject Compensation, and Research Related Injuries

There is no cost to subjects for the research tests, procedures, and study product while taking part in this trial. Procedures and treatment for clinical care may be billed to the subject, subject's insurance, or third party.

If it is determined by the site PI that an injury occurred to a subject as a direct result of the tests or treatments that are done for this trial, then referrals to appropriate health care facilities will be provided to the subject. Study personnel will try to reduce, control, and treat any complications from this trial. Immediate medical treatment may be provided by the participating site. No financial compensation will be provided to the subject by the ARLG, NIAID, NIH, by the participating sites, or other sponsors for any injury suffered due to participation in this trial.

10 STATISTICAL CONSIDERATIONS

10.1 Study Hypotheses

The study does not include formal hypothesis testing for the three primary endpoints.

10.2 Sample Size Considerations

The sample size for Stage 2 (Stage 2a/2b) was determined using the DOOR outcome measure. The sample size was calculated to provide desired precision of the estimate of the DOOR probability in order to describe the benefit to risk profile of a single dose of IV bacteriophage in clinically stable CF subjects with *P. aeruginosa* in expectorated sputum. If the true DOOR probability comparing IV bacteriophage and placebo is 70%, when the total sample size in each arm is 20 (combining subjects from Stages 2a and 2b), the two-sided normal approximate 95% confidence interval for DOOR probability is calculated at 51% and 89%, respectively, with the lower limit larger than 50% (see Section 10.5.5).

An interim analysis will be performed when the 8 subjects per arm in Stage 2a ($40\% = 8/20$) have completed their Day 8 + 3 days Follow-up Visit (Section 10.4.2). Based on the observed data, two of the doses of IV bacteriophage therapy will be dropped from the study at the interim analysis, and the planned sample size will be re-evaluated as to whether it provides the desired precision of estimates of the DOOR probability for a selected dose and placebo. If necessary, after completion of Stage 2a and per details in Section 10.4.2, the sample size will be increased up to 17 subjects for each of the two arms in Stage 2b (a total of up to 25 for the placebo arm and up to 25 for the selected bacteriophage dose in Stage 2).

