$$\hat{B} = \hat{B}_1 - \frac{1}{n_1 - 1} \sum_{j=2}^D p_{2j} \left[ q_{1j} \sum_{i=1}^{j-1} p_{1i} - \left( \sum_{i=1}^{j-1} p_{1i} \right)^2 \right] - \frac{1}{4(n_1 - 1)} \sum_{j=1}^D p_{2i} p_{1i} q_{1i}$$

where

$$\hat{B}_1 = \sum_{j=2}^D p_{2j} \left[ \sum_{i=1}^{j-1} p_{1i} + \frac{p_{1j}}{2} \right]^2 + \frac{p_{11}^2 p_{21}}{4}$$

In the equations for A and B above, D is the number of DOOR outcome ranks in the dataset;  $p_{1i}$ , for  $i = 1, 2, \dots, D$ , represents the proportion of subjects randomized to placebo with the  $i^{\text{th}}$  rank category of DOOR;  $p_{2j}$ , for  $i = 1, 2, \dots, D$ , represents the proportion of subjects randomized to IV Bacteriophage with the  $j^{\text{th}}$  value of DOOR; and  $q = 1 - p$  in general.

Additionally, the equation for an unbiased estimate of  $\zeta(1 - \zeta)$  is given by:

$$\frac{(n_1 n_2 - n_1 - n_2 + 2)\hat{\zeta} - n_1 n_2 \hat{\zeta}^2}{(n_1 - 1)(n_2 - 1)} + \frac{\hat{A}}{n_1 - 1} + \frac{\hat{B}}{n_2 - 1}$$

After substituting the values of A, B and  $\zeta(1 - \zeta)$  in the equation  $\theta$  to obtain an estimate  $\hat{\theta}$  of  $\theta$ ,  $\theta$  is defined as follows: If  $\hat{\theta} < 0$  then  $\theta = 0$ , if  $\hat{\theta} > 1$  then  $\theta = 1$ , otherwise  $\hat{\theta} = \theta$ .

We now compute the pivotal quantity  $Z_H^2 = (\hat{\zeta} - \zeta)^2 / \hat{V}$ .

$$\gamma = (n_1 + n_2 - 1) - (n_1 + n_2 - 2)\hat{\theta}$$

The CI is obtained as the solution set in  $\zeta$  of the quadratic inequality:

$$n_1 n_2 \frac{(\hat{\zeta} - \zeta)^2}{\gamma \zeta (1 - \zeta)} \leq \chi^2(1, 1 - \alpha)$$

Let,  $C = \gamma \chi^2(1, 1 - \alpha) / (n_1 n_2)$ . The CI is given as:

$$\frac{C + 2\hat{\zeta} \pm [C^2 + 4C\hat{\zeta}(1 - \hat{\zeta})]^{1/2}}{2(C + 1)}$$

The superiority of IV bacteriophage vs placebo is concluded if the lower bound of the 95% CI for the DOOR probability is larger than 50%.

Due to the presence of missing data, IPW will be used to handle missing data. For the sensitivity analysis of DOOR, IPW method will be used (see Section 8.1.3.1).

The DOOR will be analyzed as follows:

- DOOR probability with corresponding 95% CI calculated using the method described in Halperin et al. [2] calculated using the greatest reduction in *P. aeruginosa* CFU/mL by Day 8 (Table 26).
- DOOR categories distribution by treatment group through Day 8 + 3 (Table 28).

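### The 51%–89% interval that justifies 20 per arm is not the Halperin interval used in the analysis; at the variance it implies, the Halperin interval is about 49%–85%

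*Protocol*

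**What the plan says.** Protocol 10.2 sizes Stage 2 on the DOOR probability and frames the aim as precision: "The sample size was calculated to provide desired precision of the estimate of the DOOR probability". The assumptions are "If the true DOOR probability comparing IV bacteriophage and placebo is 70" per cent and "when the total sample size in each arm is 20 (combining subjects from Stages 2a and 2b"). The result given there is: "two-sided normal approximate 95% confidence interval for DOOR probability is calculated at 51% and 89%, respectively, with the lower limit larger than 50" per cent. Protocol 10.5.5, to which that sentence points, names no interval method. SAP section 5 gives the same 51% and 89%, now for 20–25 per arm.

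For the analysis, SAP 8.1.3 lists the "DOOR probability with corresponding 95% CI calculated using the method described in Halperin et al. [2"] and prints the closed form, a quadratic (score-type) interval. The same section attaches a conclusion to that interval: "The superiority of IV bacteriophage vs placebo is concluded if the lower bound of the 95% CI for the DOOR probability is larger than 50" per cent. SAP 8.1.3.1 and the footnotes to the DOOR tables repeat this rule.

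Neither document states the variance or the rank distribution behind 51%–89%, and neither gives a Halperin interval at the planned size.

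**The concern.** The interval is defined in two ways. Planning uses an interval symmetric about 70%. The analysis uses one that is pulled towards 50%, because it evaluates the binomial-type factor ζ(1−ζ) at each candidate value rather than at the estimate. Against 50% that factor is 0.25, whereas at 70% it is 0.21.

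The difference falls where the plan puts its weight. A lower limit above 50% is the feature that the sample-size text stresses, and it is also the SAP's rule for concluding superiority. If it holds for the planning interval but not for the analysis interval, the written case for 20 per arm does not describe the analysis that will be done.

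**Working it through.** **Inputs.** DOOR probability 0.70, 20 per arm, two-sided 95%, normal-approximate limits 0.51 and 0.89 (Protocol 10.2); Halperin formula with γ = (n₁+n₂−1) − (n₁+n₂−2)θ and C = γ·χ²/(n₁n₂) (SAP 8.1.3). The variance is not stated, so it is back-solved.

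**1. The plan's own figure.** 0.70 ± 0.19 gives 0.51–0.89, so SE = 0.19/1.96 = 0.0969. Half-widths of 0.185–0.195 round to the same limits, giving SE 0.0944–0.0995. Standard variances do not reproduce 51–89 with a normal quantile. The null Wilcoxon-Mann-Whitney variance, 41/(12×400), gives 51.9%–88.1%; the upper bound 0.21/20 gives 49.9%–90.1%. The null variance with a t quantile on 38 df gives 51.3%–88.7%, which does round to 51–89, but the plan says normal.

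**2. Halperin at the same variance.** C = 3.8415 × SE²/0.21 = 0.19²/0.21 = 0.1719 (γ = 17.9, θ = 0.555).

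Limits = [C + 2ζ̂ ± √(C² + 4Cζ̂(1−ζ̂))] / [2(C+1)] = [1.5719 ± √(0.0296 + 0.1444)] / 2.3438 = [1.5719 ± 0.4171] / 2.3438 = **49.3% to 84.9%**.

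| Half-width behind 51–89 | SE | Halperin, 20 per arm |
|---|---|---|
| 0.185 | 0.0944 | 49.8%–84.6% |
| 0.190 | 0.0969 | 49.3%–84.9% |
| 0.195 | 0.0995 | 48.7%–85.1% |

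**3. When the lower limit clears 50%.** The condition is ζ̂ > 0.5 + 0.5√C. With C = 0.1719 this is 0.5 + 0.5 × 0.4146 = 0.707 (0.702–0.713 over rounding). At ζ̂ = 0.70 it requires C < 0.2²/0.25 = 0.16, that is, a half-width below √(0.16 × 0.21) = 0.183, or SE below 0.0935.

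**4. Larger arms.** Scaling the variance by 20/n gives a Halperin lower limit of 49.8% at 21 per arm and 50.2% at 22. At 25 per arm the interval is 51.5%–83.7%. Even the normal interval at 25 is 53.0%–87.0%, so one interval cannot describe the SAP's whole range of 20–25.

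**5. How extreme the implied variance is.** The ceiling is √(0.21/20) = 0.1025, against 0.0969. As an illustration outside the documents, rank proportions were drawn at random for both arms, keeping draws with a DOOR probability within 0.005 of 0.70. The median normal half-width was 0.157 with four ranks and 0.150 with three (no related SAE). These correspond to SEs of 0.080 and 0.077 and Halperin lower limits of about 53% and 54%. About 1% of draws fell below 50% (0.8% and 0.7%).

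**6. An inconsistency in the printed formulas.** SAP 8.1.3 prints V with n₁+n₂+1 but γ with n₁+n₂−1. The exact variance without ties is [ζ(1−ζ) + (n₂−1)(A−ζ²) + (n₁−1)(B−ζ²)]/(n₁n₂). Substituting the SAP's own θ gives ζ(1−ζ)[(n₁+n₂−1) − (n₁+n₂−2)θ]/(n₁n₂), so the −1 form is the consistent one and is used above. Solving θ from the printed V instead (41 − 38θ = 17.9, θ = 0.608) and then using the printed γ (15.9) gives 50.5%–84.2%, with a lower limit of 49.9%–51.0% over rounding.

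**The case against.** The strongest objection is that the 49% rests on a variance that neither document states. The Halperin interval takes θ from the observed rank proportions, so its lower limit depends on the DOOR distribution, not on an SE recovered from two rounded percentages. With ties across four ranks the variance is usually smaller and the lower limit clears 50%. With the null Wilcoxon variance the Halperin interval is 50.2%–84.4%. This stands, and it makes the finding conditional.

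Second, the declared aim is precision, and at equal variance the Halperin interval is narrower: 35.6 points against 38. This also stands. Only the statement about the lower limit fails, by 0.7 point (0.2–1.3 over rounding).

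Third, 20 per arm was provisional. Protocol 10.4.2 and SAP 6.6 re-evaluate it after Stage 2a, and SAP 8.3 simulates 10,000 datasets at 20 and at 25 per arm. That is a better basis for the final size, and 25 per arm clears 50% even at the implied variance. It does not correct the figure in Protocol 10.2 and SAP 5. SAP 6.5 also expects missing data, and no inflation of n is stated.

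Fourth, planning with a labelled normal approximation and analysing with a better small-sample interval is common, and both documents disclaim formal testing. Nothing in 0.70 ± 0.19 is miscalculated. But the SAP concludes superiority from the lower bound, so the interval that supplies that bound matters.

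A reader might infer that 20 per arm cannot meet the 50% rule, or that the trial will miss it. The documents do not support that: they give no rank distribution, and most plausible ones put the Halperin lower limit at 70% above 50%.

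**Conclusion.** The mismatch of methods is in the text and needs no assumption. Its size does: if the variance is the one implied by 51%–89% with a normal quantile, the Halperin interval at 20 per arm is about 49%–85%, and its lower limit is below 50% throughout the rounding range. The planning value of 70% then falls just short of the smallest qualifying estimate, about 0.707. The shortfall is small, it rests on a back-solved variance close to its maximum, and it uses the −1 form of γ. The conclusion is that the written justification does not carry over to the planned interval. It is not a finding that the sample size is inadequate. Because the answer moves across 50% with modest changes of variance or formula, the plan should state its basis.

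**What to change.** In Protocol 10.2 and SAP section 5:

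- State the assumed DOOR rank distribution in each arm, or the variance.
- Replace 51%–89% with the Halperin interval it yields, at 20 and at 25 per arm separately.
- Keep the statement that the lower limit exceeds 50% only where that interval supports it. If the variance behind 51%–89% is retained, state about 49%–85% at 20 per arm and about 51.5%–84% at 25.
- Give the smallest estimate that meets the 50% rule at 20 per arm.

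In SAP 8.1.3, reconcile n₁+n₂+1 in V with n₁+n₂−1 in γ.

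A stated rank distribution is the better basis, since a back-solved variance only replaces one unexplained figure with another. Enrolment, endpoint and analysis method do not change. The cost is a few restated sentences and possibly a less favourable figure.

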10.3 Treatment Assignment Procedures

10.3.1 Randomization Procedures

According to a computer generated, randomized allocation list using permuted block design, in Stage 2a, subjects will be randomly assigned to one of four arms: one of three IV bacteriophage doses or placebo in a 1:1:1:1 allocation. In Stage 2b, subjects will be randomly assigned to one of two arms: the selected IV bacteriophage dose after interim analysis or placebo in a 1:1 ratio.

The list of randomized allocations will be generated by statisticians at the SDCC (The Emmes Company). The SDCC will assign each subject a randomization code and assignment from the list. The randomization code will be released at the Baseline Visit according to Appendix A.

Instructions for use of the enrollment module are included in the EDC System User's Guide.

10.3.2 Masking Procedures

A double-blind/masking technique will be used in Stage 2 of the study. The three IV bacteriophage doses and placebo will be packaged identically for administration so that treatment blind/masking is maintained. The subject and the investigator or delegate(s) who are involved in the treatment or clinical evaluation of the subjects will be unaware of the treatment group

assignments. The study investigational pharmacist will remain unblinded throughout the study and will be informed of the appropriate dose for subjects according to procedures detailed in the MOP.

To maintain the overall quality and legitimacy of the clinical trial, randomization code breaks should occur only in exceptional circumstances when knowledge of the actual treatment is absolutely essential for further management of the subject. Investigators are encouraged to discuss with the study team if he/she believes that unblinding is necessary.

The investigator is encouraged to maintain the blind as much as possible. The actual allocation must NOT be disclosed to the subject and/or other study personnel including other site personnel, monitors, corporate sponsors or project office staff. There should not be any written or verbal disclosure of the code in any of the corresponding subject documents.

The investigator must report all code breaks (with reason) as they occur on the corresponding CRF page.

Unblinding will not be in and of itself a reason for termination from the study.

10.4 Planned Interim Analyses

There will be one planned interim analysis of the primary endpoints after all subjects in Stage 2a have completed their Day 8 + 3 days Follow-up Visit, or sooner if early withdrawal. Enrollment will be held until the dose for Stage 2b is determined from the planned interim analysis. The statistical methods for the interim analysis will be fully specified in advance in a statistical analysis plan (SAP).

10.4.1 Interim Safety Review

The DSMB will evaluate safety at pre-specified intervals. Ongoing review and summary of subjects' safety will occur to allow for early detection of a safety signal that may result from an AE. The DSMB will advise the trial sponsor on whether to continue, modify, or terminate the trial based on risk assessment.

10.4.2 Interim Microbiological Activity Review

An interim analysis will be performed to select the IV bacteriophage dose with the most favorable benefit to risk profile compared to placebo for further evaluation in Stage 2b, and to exclude proceeding with bacteriophage doses that do not reduce pseudomonal colony counts or are associated with safety issues, when all subjects in Stage 2a have completed their Day 8 + 3 days Follow-up Visit or last study visit if early withdrawal.

Continuous variables will be summarized by number of subjects, mean, standard deviation (SD), median, quartiles (1st and 3rd quartiles), minimum, and maximum values. Categorical variables will be summarized by number and percentage of subjects. The interim analysis will consist of a quantitative evaluation of potential effect sizes and associated precision using a predicted intervals and predicted interval plots approach.²⁹ Briefly, predicted intervals for DOOR probability will be calculated under a range of assumptions including: (1) the trends in outcomes

observed at interim analysis will continue to end of study, (2) both DOOR distributions are identical, and (3) best and worst case scenarios for remaining outcomes. By relying on prediction intervals, no statistical hypothesis testing is required and no power is lost at interim analysis. In addition, as supplementary information, (predictive) conditional power will be calculated to quantify the probability of rejecting the null hypothesis, i.e., DOOR probability $\leq 50\%$, at the final analysis under a range of assumptions.

Similar to DOOR, changes in $\log_{10} P. aeruginosa$ CFU/mL (total and each morphology) in sputum cultures from administration of IV bacteriophages through Day 8 + 3 days, will be evaluated, using predicted interval plots to assess the precision for measuring differences in \log_{10} CFU/mL count.

The planned sample size (20 subjects per Stage 2b arm) will be reevaluated after completion of Stage 2a. If necessary, the sample size will be increased up to 25 subjects for the two arms in Stage 2b (up to 25 subjects for the placebo arm and up to 25 subjects for the selected bacteriophage dose) to provide the desired precision of estimates.

An unblinded statistician at the SDCC will report to the PHAGE Advisory Group. The PHAGE Advisory Group will make a recommendation to the DMID on the sample size (see Section 10.2) and the optimal dose to be considered for Stage 2b. This will only be a recommendation. Ultimately, DMID will review the recommendation and make the final decision on how to proceed regarding Stage 2b. Blinding to treatment assignment will be maintained at all investigational sites, and the results of the interim analysis will not be shared with the site investigators prior to the completion of the trial. The DMID will receive recommendations throughout the trial from the DSMB. DMID is responsible for deciding actions based upon the recommendations of the DSMB.

The blinded statistician at the SDCC will be involved in SAP revisions before and after the interim analysis and before the final analysis as part of the study team. This blinded statistician will be involved in discussions regarding modifications to the protocol, statistical methods, identification of protocol violations, or data validation efforts that occur after the interim analysis. A separate unblinded statistician at the SDCC who reports to the PHAGE Advisory Group will perform the interim analyses and generate the interim report but will not be involved in discussions about modifications to the protocol, statistical methods, identification of protocol violations, or data validation efforts.

